### Sample Size

While even the largest cohort with millions of patients is not guaranteed to result in a robust clinical prediction model if no relevant input variables are included (“garbage in, garbage out” – do not expect to predict the future from age, gender, and body mass index), the relationship among predictive performance and sample size is certainly directly proportional, especially for some data-hungry ML algorithms. To ensure generalizability of the clinical prediction model, the sample size should be both representative enough of the patient population, and should take the complexity of the algorithm into account. For instance, a deep neural network – as an example of a highly complex model – will often require thousands of patients to converge, while a logistic regression model may achieve stable results with only a few hundreds of patients. In addition, the number of input variables plays a role. Roughly, it can be said that a bare minimum of 10 positive cases are required per included input variable to model the relationships. Often, erratic behavior of the models and high variance in performance among splits is observed when sample sizes are smaller than calculated with this rule of thumb. Of central importance is also the proportion of patients who experience the outcome. For very rare events, a much larger total sample size is consequentially needed. For instance, a prediction based on 10 input features for an outcome occurring in only 10% of cases would require at least 1000 patients including at least 100 who experienced the outcome, according to the above rule of thumb. In general and from personal experience, we do not recommend developing ML models on cohorts with less than 100 positive cases and reasonably more cases in total, regardless of the rarity of the outcome. Also, one might consider the available literature on risk factors for the outcome of interest: If epidemiological studies find only weak associations with the outcome, it is likely that one will require more patients to arrive at a model with good predictive performance, as opposed to an outcome which has several highly associated risk factors, which may be easier to predict. Larger sample sizes also allow for more generous evaluation through a larger amount of patient data dedicated to training or validation, and usually results in better calibration measures.

For this study, based on our expertise and on the rules of thumb mentioned above, we estimate that a minimum of 250 patients with positive outcome are required to extract generalizable features. With an incidence of these outcomes of

around 10% that means that a minimum of 2500 patients are required for training. For adequate evaluation of calibration at external validation, we estimate that – as a bare minimum – another 1500 patients (thus, approximately 150 with positive outcomes) will be required. Thus, in total, we estimate that **4000 patients** are necessary to arrive at a robust model. More data will likely lead to greater performance and better calibration.

### Predictive Modeling

A KNN imputer will be co-trained to impute any missing data that may occur in future application of the model. If there is missing data in the training set, it will be imputed using said KNN imputer. Features or patients with a missingness greater than 25% will be excluded. Data will be standardized and one-hot-encoded. In case of major class imbalance – which is expected for the abovementioned endpoint – random upsampling or synthetic minority oversampling (SMOTE) will be applied to the training set. All features will initially be provided to the model for training. If necessary, we will apply recursive feature elimination (RFE) to select input features on the training data.

We will trial the following algorithms for binary classification: Generalized linear model (GLM), generalized additive model (GAM), stochastic gradient boosting machine (GBM), naïve Bayes classifier, artificial neural network, support vector machine (SVM), and random forest. Each model will be fully trained and hyperparameter tuned where applicable. The final model will be selected based upon AUC, sensitivity, and specificity, as well as calibration metrics on the resampled training performance. Training will occur in repeated 5-fold cross-validation with 10 repeats.

The one final model will then be assessed on the external validation data only once. 95% confidence intervals for external validation metrics will be derived using the bootstrap.

The threshold for binary classification will be identified on the training data alone using the AUC-based “closest-to-(0,1)-criterion” or Youden’s index to optimize both sensitivity and specificity. All analyses will be carried out in R Version 3.6.2.

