### Evaluation

The performance of classification models can roughly be judged along two dimensions: Model discrimination and calibration. The term *discrimination* denotes the ability of a prediction model to correctly classify whether a certain patient is going to or is not going to experience a certain outcome. Thus, discrimination describes the accuracy of a binary prediction – yes or no. *Calibration*, however, describes the degree to which a model’s predicted probabilities (ranging from 0% to 100%) correspond to the actually observed incidence of the binary endpoint (true posterior). Many publications do not report calibration metrics, although these are of central importance, as a well-calibrated predicted probability (e.g. your predicted probability of experiencing a complication is 18%) is often much more valuable to clinicians – and patients! – than a binary prediction (e.g. you are likely not going to experience a complication).

Resampled training performance as well as performance on the external validation set will be assessed for discrimination and calibration. In terms of discrimination, we will evaluate AUC, accuracy, sensitivity, specificity, positive predictive value (PPV), negative predictive value (NPV), and F1 Score. In terms of calibration, we will assess the Brier score, expected-observed (E/O)-ratio, calibration slope and intercept, the Hosmer-Lemeshow goodness-of-fit test, as well as visual inspection of calibration plots for both datasets, which will also be included in the publication.

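### Upsampling or SMOTE with no return to the original prevalence will inflate predicted risks, against the plan's aim of a well-calibrated model

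*Combined protocol and SAP*

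**What the plan says.** The Predictive Modeling section makes rebalancing conditional on major class imbalance, "which is expected for the abovementioned endpoint". In that case "random upsampling or synthetic minority oversampling (SMOTE) will be applied to the training set". No target event share is given, and the section does not say whether rebalancing happens before or inside the cross-validation folds.

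The same section states: "The final model will be selected based upon AUC, sensitivity, and specificity, as well as calibration metrics on the resampled training performance". It continues: "The one final model will then be assessed on the external validation data only once". On classification it says: "The threshold for binary classification will be identified on the training data alone".

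Calibration has a prominent place elsewhere. The Evaluation section holds that "a well-calibrated predicted probability (e.g. your predicted probability of experiencing a complication is 18%) is often much more valuable to clinicians" than a yes/no prediction. It lists the Brier score, E/O ratio, calibration slope and intercept, the Hosmer-Lemeshow test and calibration plots. The Sample Size section sizes the external set for this purpose: "For adequate evaluation of calibration at external validation, we estimate that", as a minimum, "another 1500 patients (thus, approximately 150 with positive outcomes) will be required". Expected Results anticipates an AUC of at least 0.70, more realistically 0.8 or above, with good calibration.

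No section describes an intercept update, a prior correction, Platt or isotonic scaling, or any other return to the original prevalence.

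**The concern.** A model fitted to data in which events have been made artificially common learns that events are common. Patient ranking, and so the AUC, is largely unaffected, but the probabilities refer to a population that does not exist. A threshold derived on the training data absorbs the shift for yes/no classification only.

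At stake is the output that the plan itself values most. The external assessment would probably show a plain calibration failure, with no planned means of repair. Expected Results does not say whether the web tool will display probabilities. If it does, patients and surgeons would see inflated surgical risks.

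**Working it through.** **Inputs from the plan.** Incidence about 10%; training set of 2500 with 250 events; external set of 1500 with about 150 events (Sample Size). AUC 0.70, more realistically 0.8 or greater (Expected Results). The plan's own figures reproduce: 250/0.10 = 2500; 1500 × 0.10 = 150; 2500 + 1500 = 4000.

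**Assumed, because not stated.** The target event share *s*, shown from 15% to 50%.

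**Shift.** Raising the event share from *p* to *s* adds logit(*s*) − logit(*p*) to the intercept of a logistic-type model. For *p* = 10% this is 0.81 at *s* = 20%, 1.35 at 30% and ln 9 = 2.20 at 50%. The calibration intercept would then be about −0.81 at 20% and −2.20 at 50%.

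**E/O by formula.** Take true risk as logit-normal, with mean *p* and spread solved to give the stated AUC. Then E/O = mean of expit(true logit + shift), divided by *p*.

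| Event share after rebalancing | AUC 0.70 | AUC 0.80 | AUC 0.90 |
|---|---|---|---|
| 15% | 1.46 | 1.41 | 1.31 |
| 20% | 1.91 | 1.79 | 1.59 |
| 30% | 2.79 | 2.51 | 2.09 |
| 40% | 3.65 | 3.21 | 2.56 |
| 50% (1:1) | 4.51 | 3.92 | 3.04 |

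An equal-variance binormal score gives the same values to within about 0.02. At 1:1 and AUC 0.70/0.80, an incidence of 5% gives 8.9/7.6, and 20% gives 2.3/2.1.

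**Brier score by formula.** At AUC 0.70: 0.085 without the shift, 0.095 at 20% events, 0.220 at 1:1. At AUC 0.80: 0.077, 0.086, 0.184.

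**The plan's own example.** A true risk of 18% has logit −1.52. Adding 0.81, 1.35 or 2.20 gives a displayed risk of 33%, 46% or 66%.

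**What the external set would show.** SE of log(E/O) ≈ √(0.9/150) = 0.077, so a calibrated model should fall within about 0.86 to 1.16. Adding the uncertainty from 250 training events gives √(0.9/150 + 0.9/250) = 0.098, or about 0.83 to 1.21. Every entry in the table lies outside both bands.

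**Simulation, logistic model and forest.** 2500 training patients, 23 features, 10% incidence, 10,000 test patients, random upsampling, linear and non-linear truth, best achievable AUC 0.72 and 0.82, 20 replicates per setting. Ratios are to the same model's E/O without resampling.

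- Logistic model: 1.7 to 1.9 at 20% events, 3.7 to 4.6 at 1:1 (E/O without resampling 0.98 to 1.00). Test Brier score at 1:1 was 0.176 to 0.225, against 0.076 to 0.087 without resampling.
- Untuned, fully grown forest: 1.20 to 1.22 at 20% events, 1.25 to 1.28 at 1:1. Its gross E/O at 1:1 was 1.37 to 1.42, of which 1.09 to 1.12 was present without resampling. Test Brier score was 0.082 to 0.091, against 0.081 to 0.090.

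**Simulation, SMOTE.** A separate logistic-model run (20 predictors, 60 repeats, AUC 0.70 to 0.80) gave E/O of 1.90 to 1.76 at 20% events and 4.33 to 3.68 at 1:1. Shifting the intercept back restored E/O to 1.01 to 1.05, but after SMOTE to 1:1 the calibration slope stayed at 0.72 to 0.77, against 0.87 to 0.92 with no rebalancing.

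**Would model selection catch it?** With upsampling inside the folds, held-out E/O was 3.7 to 4.6 for the logistic model and 1.37 to 1.43 for the forest, so the error is visible. If the data are upsampled to 1:1 before the folds are drawn, mean prediction and event share in the held-out folds are both about 50% for a logistic model. E/O is then about 1 and the error is hidden.

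**The case against.** The best counter-argument is that the size is unknown. The plan fixes neither the event share nor the algorithm, and five of its seven candidates were not simulated. At AUCs above 0.80, which the plan considers likely, the inflation is smaller. For a fully grown forest the Brier score hardly moves, and dropping resampling cost that forest 0.013 to 0.021 in AUC. The plan also selects on calibration metrics, which could penalise the worst models, and it would publish E/O, intercept, slope and plots, so the error would be disclosed.

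Much of this stands as a limit on size. The figures belong to logistic-type models and one kind of forest, and the event shares are assumptions. It does not change the direction. At AUC 0.90 a logistic-type model still gives E/O of about 1.6 at 20% events and 3.0 at 1:1, and the forest's gross E/O at 1:1 also exceeds the wider band of 0.83 to 1.21. Selection on calibration chooses among candidates all trained on rebalanced data and corrects none of them; it may miss the error altogether if rebalancing precedes the folds. Disclosure after a single external assessment is not repair. The condition for rebalancing is one that the plan itself expects to be met.

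**Conclusion.** The concern holds and should be settled before the models are fitted. Followed as written, the plan would produce predicted risks that are too high, although it treats calibration as a central aim. At 10% incidence and AUC 0.70 to 0.80, a logistic-type model would overstate risk by a factor of 1.9 to 1.8 at an assumed 20% event share and 4.5 to 3.9 at an assumed 1:1 ratio. The simulated forest was inflated by about 1.2 to 1.3 times its unresampled E/O. No size is claimed for the other algorithms. Confidence is high in the direction and in the size for logistic-type models; the size for the model eventually selected cannot be known until its event share and algorithm are fixed.

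**What to change.** **Preferred.** State in Predictive Modeling that all candidates are fitted on the original class distribution, and that imbalance is handled through the training-derived threshold. This removes a step and needs no new data. It may cost some tree-based models a little AUC (0.013 to 0.021 for the simulated forest; none for the logistic model).

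**If resampling is kept**, the plan should:

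1. State the target event share.
2. Resample only the training part of each cross-validation fold, and compute selection metrics on held-out patients who have not been resampled.
3. Recalibrate both intercept and slope by a cross-fitted (nested) procedure. An intercept shift alone is enough for a randomly upsampled logistic model but not for SMOTE. Cross-fitting matters because recalibrating and scoring on the same out-of-fold predictions gave E/O of 1.000 and slope of 1.000 to 1.002 for both simulated models by construction; cross-fitting gave slopes of 0.959 to 0.989.
4. Let slope, Brier score and calibration plots separate the candidates, since E/O and intercept will sit near 1 and 0 after recalibration.
5. Freeze the recalibration before the single external assessment, and use the recalibrated probabilities for the external calibration metrics and for any probability that the web tool shows.

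In simulation a recalibration frozen before testing gave test E/O of 0.98 to 1.00 and Brier scores of 0.077 to 0.089, close to no resampling (0.076 to 0.090).

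Either route takes two or three sentences of text. The second also adds computing work: a nested loop for each candidate algorithm and each of the three endpoints.

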### Input Feature Definitions

All features are measured preoperatively. Recorded baseline variables will include age, gender, maximum aneurysm diameter, anatomical location (artery), total number of aneurysms per patient, if multiple aneurysms were treated

during the index session, calcification of the aneurysm wall or neck, aneurysm morphology (saccular, dissecting, fusiform, or other), involvement of critical perforating or branch vessels, and intraluminal thrombosis.

We will also capture prior SAH, mRS at admission, prior aneurysm treatment, presence of anticoagulation/antiplatelet therapy preoperatively, and hypertension, as well as American Society of Anesthesiologists (ASA) grading, the PHASES, ELAPSS, and UIATS scores including the UIATS “pro-repair” and “pro-conservative treatment” subscores. The unruptured intracranial aneurysm treatment score (UIATS) consists of two subscores: One that represents the strength of recommendation for invasive repair of an unruptured aneurysm, and one that represents the strength of recommendation for conservative management of an unruptured aneurysm. The final overall UIATS score is subsequently calculated as the difference between the two subscores. Also included was the surgical approach: minimally invasive or standard approach, and whether a bypass was performed.

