### **Expected Results**

We expect to arrive at a generalizable model based on multicenter international data that is likely to predict the abovementioned binary outcomes consistently with an AUC of at least 0.70 (more realistically 0.8 or greater) and that is well-calibrated. A web-based prediction tool will also be created for each of the two models using the *shiny* environment, much akin to e.g. <https://neurosurgery.shinyapps.io/impairment>. This web-based app will be available for free on any internet-capable device (mobile or desktop), and should be stable on most devices due to the server-based computing. The costs for maintaining the server will be carried by the sponsor.

The collected data will be stored by the sponsor for 10 years. The large dataset will be open to further analysis and will be provided to any of the contributing centers at reasonable request and after approval by all other centers. The goal is to enable other analyses using the collected dataset. If any additional analyses lead to publication, all contributors will be included as co-authors and all co-authors will have the opportunity to review said manuscript beforehand. Any contributing study center has the right to veto publication of any subsequent analyses that includes their data.

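### The plan names no penalty for the all-feature GLM; if it is fitted without one, expect a calibration slope of about 0.7 to 0.9, which a log-loss-tuned penalty on data that are not upsampled corrects on average.

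*Combined protocol and SAP*

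**What the plan says.** - **Candidates.** Predictive Modeling opens its list of seven algorithms with "Generalized linear model (GLM), generalized additive model (GAM), stochastic gradient boosting machine (GBM". Hyperparameters are tuned where the algorithm has any. No penalty or shrinkage is named for the GLM, and none is ruled out.
- **Features.** "All features will initially be provided to the model for training". Recursive feature elimination (RFE) may follow if needed. Data are standardised and one-hot encoded.
- **Class imbalance.** The same section expects major imbalance and applies upsampling or SMOTE to the training set. It does not say whether this comes before or inside cross-validation, and it plans no recalibration.
- **Size.** Sample Size asks for "a minimum of 250 patients with positive outcome are required to extract generalizable features", which at 10% incidence is 2500 training patients. For external validation, "another 1500 patients (thus, approximately 150 with positive outcomes) will be required". Its rule of thumb: "Roughly, it can be said that a bare minimum of 10 positive cases are required per included input variable".
- **Inputs.** The list in Input Feature Definitions begins "Recorded baseline variables will include age, gender, maximum aneurysm diameter, anatomical location (artery), total number of aneurysms per patient". It includes the UIATS total and both UIATS subscores, and defines the total as the difference between the two.
- **Aim.** Expected Results looks for an AUC of at least 0.70, more realistically 0.8 or above, from a model that generalises "and that is well-calibrated". Interpretability commits to publishing the parameters if a GLM is chosen.

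**The concern.** Maximum-likelihood coefficients fitted with few events per column are too large on average. In new patients the high risks then come out too high and the low risks too low, and the calibration slope falls below 1. Sparse one-hot levels (artery, morphology) add to this.

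The stake is the predicted probability itself. The Evaluation section says that a calibrated probability is often worth more to clinicians and patients than a yes/no prediction, and the result is to become a public web tool. External validation is run once, so overfitting first seen there can be reported but not repaired. The GLM is also among the easiest candidates to publish and check. If its penalty is left open, it either competes in a weaker form than it need have, or is released with over-extreme risks.

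This does not call for more patients. It concerns how the planned patients are used.

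**Working it through.** **1. The plan's own figures.** 250 / 0.10 = 2500 for training; 1500 × 0.10 = 150 events for validation; 2500 + 1500 = 4000. All reproduce.

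**2. Events per column.** Input Feature Definitions lists 10 features in its first paragraph and 13 in its second (11 clinical items and scores, 2 surgical), so 23.
- 250 / 23 = 10.9 events per feature, just above the plan's rule of 10.
- The column count after encoding is not given. I assume 23 to 40. Morphology alone has four categories and location is by artery, so the low end is optimistic unless RFE removes columns.
- 250 / 32 = 7.8 and 250 / 40 = 6.3. Applied per column, the rule of 10 would need 320 or 400 events.

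**3. Expected shrinkage by formula.** S = LR / (LR + p), with LR = −n ln(1 − R²), n = 2500, and R² (Cox-Snell) derived from the AUC at 10% incidence with a normally distributed linear predictor.
- AUC 0.70: R² = 0.047, LR = 120. S = 120/143 = 0.84 (p = 23); 120/152 = 0.79 (p = 32); 120/160 = 0.75 (p = 40).
- AUC 0.80: R² = 0.110, LR = 292. S = 292/315 = 0.93; 292/324 = 0.90; 292/332 = 0.88.

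**4. Simulation without resampling.** 80 training sets per setting, n = 2500, 10% events; correlated continuous and binary predictors, half with true effects; each fit tested on 40,000 new patients. Ridge penalty tuned by log-loss in 5-fold cross-validation (2 repeats). Entries are mean slope (mean AUC).

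| Columns | True AUC | S by formula | Plain GLM | Ridge |
|---|---|---|---|---|
| 23 | 0.70 | 0.84 | 0.81 (0.684) | 1.05 (0.688) |
| 23 | 0.80 | 0.93 | 0.88 (0.790) | 1.02 (0.792) |
| 32 | 0.70 | 0.79 | 0.75 (0.678) | 1.05 (0.680) |
| 32 | 0.75 | 0.86 | 0.82 (0.732) | 1.03 (0.733) |
| 32 | 0.80 | 0.90 | 0.85 (0.786) | 1.01 (0.786) |
| 40 | 0.70 | 0.75 | 0.68 (0.673) | 1.06 (0.677) |
| 40 | 0.80 | 0.88 | 0.79 (0.781) | 1.01 (0.782) |

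- The plain slope was below 0.9 in 54% to 100% of data sets.
- Mean AUC changed by +0.0004 to +0.0046 with ridge.
- Lasso at 32 columns gave slopes of 1.02 and 0.99.
- Two other simulations with different predictor sets gave plain slopes of 0.72 to 0.89 and 0.71 to 0.91, and ridge slopes of 0.96 to 1.03 and 0.96 to 1.01.
- As an illustration, with 38 assumed columns, patients given a plain-GLM risk above 30% had a mean prediction of about 42% to 43% and an observed rate of 34% to 37%.

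**5. Limits of the remedy.** Ridge slopes still vary: the 5–95% ranges run from 0.80 to 1.39 over the settings, and 10% to 39% of fits had a slope above 1.1. AUC fell slightly in 4% to 31% of data sets. The mean distance of the slope from 1 nevertheless fell in every setting, for example from 0.323 to 0.144 (40 columns, AUC 0.70) and from 0.125 to 0.072 (23 columns, AUC 0.80). Tuning on AUC instead of log-loss overshrank, to a mean slope of 1.21 at 23 columns and AUC 0.70.

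**6. With the planned resampling.** Random upsampling to 50:50 (assumed ratio) multiplies the odds by (0.5/0.5) / (0.1/0.9) = 9. A patient at 10% risk is then given 50%. In simulation, mean predicted risk was 3.7 to 4.4 times the observed rate with the plain GLM and 3.7 to 4.5 times with ridge. When the penalty was tuned on already upsampled data, the slope moved only from 0.63–0.85 to 0.69–0.89. In a separate run with resampling inside folds, ridge reached 0.83 to 0.96, with the inflation unchanged.

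**7. UIATS.** Total = (one subscore) − (the other). Standardising keeps this linear dependence, so with all three entered an unpenalised GLM has no unique coefficients for them. Predicted risks do not suffer from this, but the parameters promised under Interpretability do.

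**The case against.** **The plan does not say that the GLM is unpenalised.** A reader might infer from the list that it is. The documents do not support that: they are silent, and the tuning sentence could cover a penalty. What stands is that the choice is unspecified, and that a GLM in its ordinary sense has no penalty to tune.

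**There are safeguards.** Selection uses calibration metrics on resampled training performance, and slope, intercept, E/O ratio and calibration plots are reported for both data sets. An over-extreme GLM can be noticed and passed over, and that would be a proper result, not an unfair one. RFE may reduce the columns. This stands in part: selection can reject a poorly calibrated fit but does not improve it, and RFE is conditional and does not shrink the coefficients that it keeps. Its effect was not simulated.

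**The pipeline as written resamples.** If it does, a penalty alone repairs little: the slope barely moves and the fourfold inflation remains. This stands in full, and the fix has to carry that condition.

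**The size may be small.** The plan thinks an AUC of 0.8 or more is realistic, and 2500 is a minimum. At AUC 0.80 with 23 columns the formula gives 0.93 and the simulation 0.88, which is mild. But 0.70 is the plan's own floor, and encoding pushes the column count up.

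**Conclusion.** The point holds as a gap in specification with a cheap and better alternative. An unpenalised all-feature GLM at about 250 events would have an expected calibration slope of roughly 0.7 to 0.9 in new patients. Log-loss-tuned ridge brings this to about 1 on average, with essentially no change in mean AUC.

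Two stronger readings are tempting and fail. One is that the released tool will give over-extreme risks for this reason: that requires the GLM to be chosen from seven candidates, unpenalised, and past the calibration checks. The other is that a penalty removes the miscalibration: it corrects the slope on average and not in every data set, and it does nothing for the inflation from upsampling.

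The figures rest on assumptions: 23 to 40 columns, 10% incidence, true AUC 0.70 to 0.80, the simulated predictor distributions and share of true effects, random upsampling to 50:50 in place of SMOTE, and fewer cross-validation repeats than planned. The direction was the same in every setting tested; the size was not.

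**What to change.** In Predictive Modeling:

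1. Name the GLM candidate as a penalised GLM (ridge or elastic net), with the penalty chosen by log-loss, not AUC, in the planned cross-validation (five folds, ten repeats), on data that are not upsampled.
2. Fit this probability model without upsampling or SMOTE. If resampling is kept, do it only inside the training folds and recalibrate to the observed incidence before risks are reported. Omitting it is cleaner. The classification threshold is already set on the ROC curve in the training data, so balanced sensitivity and specificity do not depend on resampling.
3. If this model is selected, publish the shrunken coefficients. With a ridge or elastic-net penalty they are defined even with all three UIATS terms entered.

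Cost: two or three sentences, no extra patients, and no computation beyond the cross-validation already planned. The drawback is that shrunken coefficients have no simple confidence intervals. The plan uses none for coefficients; its bootstrap intervals are for the external validation metrics and are unaffected.
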